1 **25/10/2022**

2

3 **Retraining the automatic reaction to physical activity and sedentary stimuli in adults 60 years of**  
4 **age or older: A cognitive bias modification protocol**

5

6 **ABSTRACT**

7 **Background:** To counteract the pandemic of physical inactivity, current interventions mainly rely on  
8 reflective processes that focus on increasing the motivation to be physically active. Yet, while these  
9 interventions successfully increase intention, their effect on actual behavior is weak. Recent findings  
10 suggest that this inability to turn the intention into action is explained by negative automatic reactions to  
11 stimuli associated with physical activity. These automatic reactions could be particularly strong in older  
12 adults, who are more likely to associate physical activity with fear, pain, or discomfort. **Objective:** The aim  
13 of this program is to test the effect of an intervention that targets the automatic processes underlying  
14 physical inactivity in older adults. Training older adults to inhibit the automatic attraction toward sedentary  
15 stimuli is hypothesized to increase physical activity, thereby contributing to improving physical functioning  
16 and quality of life. **Methods:** To test these hypotheses, older adults will be enrolled in a controlled double-  
17 blinded study with a 1, 3, 6, and 12-month follow-up. Participants will be randomized (1:1 ratio) to receive  
18 a 12-session cognitive-bias modification training for 3-week based on a go/no-go task in an experimental  
19 or a control condition (placebo). The primary outcome will be the number of steps per week. Secondary  
20 outcomes include automatic approach-avoidance tendencies, explicit affective attitudes toward physical  
21 activity, physical function, and quality of life. **Discussion:** The study is expected to inform public-health  
22 policies and improve interventions aiming to counteract the pandemic of physical inactivity.

23

24 **KEYWORDS:** Attentional Bias, Aging, Exercise, Sedentary Behavior

25 **Background**

26 Over the past two decades, society has encouraged people to be more physically active [1-3]. As a  
27 result, most individuals are now aware of the positive effects of regular physical activity and have the  
28 intention to exercise [4]. Yet, this intention is not sufficient, as exercise plans are often not executed [5].  

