53 with fear, pain, or discomfort felt during physical exercise. Therefore, older adults could be particularly  
54 responsive to and benefit the most from an intervention targeting the automatic reactions to physical activity  
55 and sedentary stimuli.

56 Interventions targeting automatic reactions to health-related stimuli have already proven to be  
57 successful in changing behavior [26-32]. For example, interventions have been used to retrain the automatic  
58 reaction to alcohol [27]. Using a joystick, patients were repeatedly asked to avoid pictures on a screen that

59 were related to alcohol and to approach pictures unrelated to alcohol. Results showed that adding to a  
60 regular treatment an intervention targeting cognitive bias reduced the relapse rates one year after treatment  
61 discharge by 9% to 13% [27-29]. These interventions have also proven to be useful in impacting smoking  
62 [30], social anxiety [31], and eating behavior [32]. Based on these encouraging results, the current project  
63 proposes to test the effect of a cognitive-bias intervention on another health behavior: physical activity.

64 **Primary aim**

65 The overall primary objective of this project is to investigate the effectiveness of an intervention  
66 targeting automatic reactions to physical activity and sedentary stimuli in older adults.

67 **Secondary aim**

[figure not shown]
68 The secondary objective is to test the effects of the intervention on reflective and automatic  
69 processes underlying physical activity, physical functioning, and quality of life.

70

71 **Methods**

72 **Study design and settings**

73 Our study follows a placebo (sham-controlled), double-blinded design with a 12-month follow-up  
74 (Figure 1).

75

**Figure 1.** Study design

76

77 ***Participants***

78 Older adults aged 60 years and older will be enrolled in the study.

79 ***Recruitment***

80 Recruitment will occur by placing posters in a: strategic areas, such as public areas where permissible and  
81 b: posting on social media (Facebook, Twitter). Interested seniors will be asked to contact the researcher  
82 directly. Once the interested person initiates the contact leaving a phone message or sending an e-mail, we  
83 will follow up on them and will invite them to attend in an in-person meeting aiming to increase their  
84 intention to be physically active based on the “Ask-Assess-Advise” approach and to inform them about the  

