140 of 400 trials for a total of 30 min. To assess the effect of the intervention, primary and secondary outcomes  
141 will be collected for one week, the week before the first session, the week following the last session of the  
142 intervention, as well as 1, 3, 6, and 12 months post intervention.

143

144 **Figure 3.** Protocol timeline.

145

146 ***Allocation and blinding***

147 Participants and research assistant will be blinded to the groups’ allocation. The participant blinding  
148 success will be appraised by asking them to guess in what group there were at the trial termination. Besides,  
149 the research assistant blinding success will be appraised via detecting the group allocation (Experimental  
150 vs. Control) by research assistant at the end of data collection phase. The randomization will be generated  
151 on a computer and an independent coworker will carry out the randomization. The participant’s  
152 identification number will be used to determine the sequence of randomization. Participants will be  
153 randomized in a 1:1 ratio between the intervention and active control condition.

154

155 ***Outcomes***

156 Participants will first respond to questions related to their age, sex (male, female), weight, and  
157 height.

158 ***Primary outcome***

159 The project focuses on device-based measures of physical activity and sedentary behaviors.  
160 Specifically, the primary outcomes collected using a physical-activity tracker will be the number of steps.  
161 Participants will be given the tracker and will be trained on how to wear the device (ie, over the right hip,  
162 affixed to an elastic belt, preferably worn under their waistbands). Currently, the waist based Actigraph is  
163 the most used device to objectively measure physical activity. Participants will be instructed to used it all

164 day long for 7 days and not to used it during shower or when they sleep at night. If the participant uses the  
165 tracker less than for 4 days in a row for at least 7 hours per day, they will not be included in the study. The  
166 number of steps measured in the week pre- and post-intervention, as well as 1, 3, 6, and 12 months after the  
167 intervention will be used as the primary outcome.

168 ***Secondary Outcomes***

169 The secondary outcomes will allow the examination of indirect health effects related to an increase  
170 in physical activity and a decrease in sedentary behavior.

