225 Statistical analyses will be performed according to the intention-to-treat principle and abide by the  
226 Consolidated Standards of Reporting Trials (CONSORT) guidelines. A sequential analysis will be  
227 conducted with an interim analysis after 50% of the data is collected and the other analyses after all data is  
228 collected [47]. Based on the Pocock boundary, the threshold for significant p-values will be .0294 [48]. If  
229 the effect is significant at the interim analysis, thereby indicating that the data provide support for the

230 hypothesis, data collection will be terminated. Mean, SD, median and range values will be used to  
231 summarize the continuous data. The primary outcome (number of steps per week) will be analyzed using  
232 multiple linear regressions. Particularly, we will test whether the participants' physical activity level  
233 (number of steps) the week after intervention termination will be higher in the intervention group relative  
234 to the control group, after adjustment for covariates (i.e., age, sex). Furthermore, we will test whether  
235 participants' automatic approach tendencies towards physical activity will be higher and participants'  
236 automatic approach tendencies towards sedentary behaviours will be lower in the intervention group  
237 compared to the control group.

238 *Secondary Analysis*

239 The continuous outcomes will be analyzed using linear mixed-effects models, which account for  
240 the nested structure of the data (i.e., multiple observations within a single participant), thereby providing  
241 accurate parameter estimates with acceptable type-I error rates [49]. To examine the effect of the  
242 intervention on the evolution of physical activity and sedentary behavior, models will include interaction  
243 terms between group (intervention group vs. comparison group) and number of days within or after (follow-  
244 up) the intervention. We will treat the continuous secondary outcomes in the similar way to the primary  
245 outcome. R software will be exploited for all analyses.

246 ***Data Monitoring***

247 The principal investigator will instruct all project team members to ensure that the study will be  
248 carried out according to the protocol. Research assistants will need to understand the protocol before  
249 starting the data collection. The ethics committee may visit the research sites for quality assurance. No  

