250 serious adverse event resulting from the intervention is expected; however, all potential adverse events will  
251 be documented.

252

253 **Discussion**

254 Most individuals are aware of the benefits to health of regular physical activity and have good  
255 intentions to exercise. Yet, 1.4 billion people worldwide are inactive, which suggests that turning intention  
256 into action can be challenging. Recent findings show that the intention-action gap could be explained by  
257 negative automatic reactions to stimuli associated with physical activity. This gap is particularly concerning  
258 in older adults, who are more likely to spontaneously associate physical activity with fear, pain, or  
259 discomfort. Current interventions targeting physical activity largely focus on providing rational information  
260 to alter individuals' conscious goals. However, these strategies have been shown to be insufficient to change  
261 a behavior and urge that automatic reactions towards physical activity-related stimuli would be involved in  
262 the physical activity regulation. Therefore, to promote physical activity, the current project proposes to train  
263 older adults to suppress their automatic attraction toward sedentary stimuli and to respond positively to

264 physical-activity stimuli. The intervention is expected to reduce physical inactivity during the intervention  
265 and at follow-up, thereby improving physical functioning. More broadly, the output of this program has the  
266 potential to develop an evidence-based, large-scale, low-cost intervention that would complement current  
267 reflective approaches in older adults to improve their quality of life. Finally, the results will inform public  
268 health policies aiming to counteract a global health problem: The pandemic of physical inactivity.

269

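### The longitudinal analysis names only group-by-days terms; with numeric days these measure change in the group difference, and no group difference at 1, 3, 6 or 12 months is specified

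*Combined protocol and SAP*

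**What the plan says.** The Secondary Analysis section uses linear mixed-effects models for continuous outcomes. To examine the effect of the "intervention on the evolution of physical activity and sedentary behavior, models will include interaction" "terms between group (intervention group vs. comparison group) and number of days within or after" the intervention, with follow-up in brackets. It does not say whether days are linear, piecewise or categorical, where time starts, or whether the pre-intervention week is a response or a covariate.

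The only week for which the Data analyses section names a group difference in steps is in the Primary analysis, which tests whether activity "the week after intervention termination will be higher in the intervention group relative" to control, adjusted for age and sex.

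Other sections look further ahead:

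- The Abstract describes a "blinded study with a 1, 3, 6, and 12-month follow-up".
- The Primary outcome section lists the "number of steps measured in the week pre- and post-intervention, as well as 1, 3, 6, and 12 months after the" intervention as the primary outcome. It includes the pre week in that list without giving it a role in a model.
- The Discussion expects less inactivity during the intervention "and at follow-up, thereby improving physical functioning".

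Secondary Outcomes, item 2(a), makes moderate-to-vigorous activity from the IPAQ-SF a control variable. That is a self-report measure, not baseline steps, and neither the visit nor the model is given.

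**The concern.** A reader of the final report will ask whether the groups still differ at 3, 6 or 12 months. A group-by-days coefficient over follow-up answers another question: whether the difference grows or shrinks. The best possible result, an effect that is fully kept, makes that coefficient zero. So the named term does not match the benefit that the Discussion expects.

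Because the coding of time is open, the same data can also give a clear interaction or none, and the choice could be made after the data are seen. At stake is the interpretation of a year of follow-up data that will be collected anyway.

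**Working it through.** **Inputs from the documents.** Effect .39 SD and 108 per arm (Sample size); 1:1 allocation; visits before training, after training, and at 1, 3, 6 and 12 months.

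**The plan's own figure.** There is none for the longitudinal analysis. The 108 per arm comes from a two-group calculation and does not follow exactly from its stated inputs. With n = 2[(z for alpha + z for power)/.39]², one-sided .05 gives 2(1.645 + 1.282)²/.1521 = 112.6, so 113; two-sided gives 2(1.960 + 1.282)²/.1521 = 138.2, so 139. An effect of .40 with a one-sided test gives 108. That is a separate matter; 108 is used here as the planned number.

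**Assumptions not in the documents.** SD 1; equal correlation ρ between any two visits, .5 to .7; complete data; two-sided .05; post-training visits at days 0, 30, 91, 182 and 365, baseline at day −28. Each visit's group difference has variance 2/108 = .01852. Power = Φ(|z| − 1.96) + Φ(−|z| − 1.96). Ranges below run from ρ = .5 to ρ = .7.

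**1. Follow-up slope, post-training visits only.** Mean day 133.6, sum of squares S = 86,285. SE = √[.01852(1 − ρ)/S] = .000328 to .000254 per day. A sustained effect has true slope 0, so rejection is 5% whatever the SD or ρ. A linear fade to half (.195) has slope −.195/365 = −.000534, so z = −1.63 to −2.11 and power 37–56%. The follow-up term of a piecewise model gives the same result.

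**2. One line including baseline.** Mean day 106.7, S = 108,047. For a sustained effect the differences are 0, then .39 five times: slope = .39 × 134.67/108,047 = .000486 per day. SE = .000293 to .000227; z = 1.66 to 2.14; power 38–57%. For the fade to half, the fitted slope is about −.00003 and power 5%.

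**3. Piecewise days (within and after), 12-month difference.** This is the training slope times its length plus 365 times the follow-up slope. Its variance is .01852(1 − ρ)[1 + 1/5 + 231.4²/86,285] = .01852(1 − ρ)(1.821), so SE = .130 to .101. Sustained: z = 3.00 to 3.88, power 85–97%.

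**4. Categorical visit, baseline as a response.** The interaction is a difference in change from baseline: SE = √[.01852 × 2(1 − ρ)] = .136 to .105. Sustained: z = 2.87 to 3.70, power 82–96%.

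**5. Visit difference adjusted for baseline.** SE = √[.01852(1 − ρ²)] = .118 to .097. Sustained: z = 3.31 to 4.01, power 91–98%. Fade to half, at 12 months: z = .195/SE = 1.65 to 2.01, power 38–52%.

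**6. Adjusted average of the four follow-ups.** Variance = .01852[(1 + 3ρ)/4 − ρ²], so SE = .083 to .073. Mean follow-up day = (30 + 91 + 182 + 365)/4 = 167. Under the fade to half the average effect is .39(1 − .5 × 167/365) = .30; z = 3.61 to 4.14; power 95–99%.

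| Quantity | Sustained .39 | Fade to half at 12 months |
|---|---|---|
| Follow-up days slope | 5% (true value 0) | 37–56% (a decline) |
| One line with baseline | 38–57% | 5% |
| Adjusted 12-month difference | 91–98% | 38–52% |
| Adjusted follow-up average | over 99% (z = 4.68 or more) | 95–99% |

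**Sensitivity, sustained effect.** At the plan's .0294 threshold, the single line has 30–49% and the adjusted visit 87–97%. With 20% missing at 12 months (86 per arm), the adjusted 12-month difference has 84–95%. With correlation falling from about .7 to .5 over the year, the single line has 39% and the adjusted visits 91–96%.

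**The case against.** The strongest case is that the text does not exclude a suitable model. The Primary outcome section lists the pre week with the outcome, which points towards baseline as a response; with categorical time, each group-by-visit term would then be a follow-up effect. The models are only said to include interaction terms, so a group term would normally be there too. With post-training data only and the origin at the end of training, that term has 89–93% power for the immediate effect. A piecewise model already carries the 12-month difference.

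This stands in part. A reader might infer that the interaction can never show a lasting effect, or that the planned model cannot estimate one. The documents do not support that: it depends on a coding they leave open. But a count of days reads most naturally as numeric, and no group term, origin or combination is named as a test.

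A reader might also infer that a significant slope would be mistaken for a lasting benefit. If the effect faded linearly to zero, the follow-up slope would be significant in 90–99% of trials. Its negative sign would correctly show decline, and evolution is the stated aim, so this is no fault of the slope.

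Finally, the Discussion states an expectation, and the Background result at one year concerns alcohol relapse. Neither commits the trial to a 12-month test. They do show that a slope alone leaves the expected benefit without a named estimate.

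**Conclusion.** The point holds on the numeric reading of days. The plan's stated longitudinal test measures change in the group difference, while the Primary outcome section and the Discussion look for an effect at follow-up. No follow-up contrast is named, and baseline steps have no stated role.

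The zero slope under a sustained effect follows from the model and needs no assumption about SD or correlation. The power figures, 38–57% for a single line against 91–98% for an adjusted visit difference, rest on the assumptions listed. The gain from adjustment alone is smaller: 91–98% against 82–96% for a difference in change from baseline. A 12-month contrast is not strong in every case, with only 38–52% power if the effect halves.

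A reader might extend this to the primary analysis. That would be wrong: the comparison in the week after training does not use these terms. The point should be settled before any unblinded data are seen, including at the interim analysis.

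**What to change.** In the mixed model, estimate the group difference at 1, 3, 6 and 12 months, adjusted for the baseline value of the outcome. Use categorical visit with group-by-visit, or a piecewise day model with a stated origin, the same baseline adjustment and the same contrasts.

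Name one key follow-up contrast and the significance threshold that applies to it. The average over follow-up keeps power better if the effect fades. It does not show persistence to 12 months, however: under a linear fade to zero it would still be .39(1 − 167/365) = .21 SD. The 12-month difference should therefore be reported beside it with a confidence interval.

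Keep the group-by-days slope as a supporting analysis of evolution, with its form and origin written down.

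The cost is SAP wording and model code; no new data are needed. The downsides are a few more parameters with about 216 participants, several contrasts that need one key contrast to limit multiplicity, and, with categorical visits, no use of off-schedule days, which the piecewise model keeps.

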## 270 **Fundings**

271 [name] is supported by the Natural Sciences and Engineering Research Council of  
272 Canada (NSERC; RGPIN-2021-03153), the Banting Research Foundation, and the Canada Foundation for  
273 Innovation (CFI). The funding sources had no role in the design of this study and will not have any role  
274 during its execution, analyses, interpretation of the data, or decision to submit results.

275

